3.3. Sample Size Considerations

For Cohort A, approximately 60 participants are planned. Assuming the true ORR is 35% for the intervention in this group, 60 participants are needed to ensure that there is at least 90% power to reject the null hypothesis of $ORR \leq 15\%$. This calculation assumes 1-sided test at the overall 0.025 level of significance.

For Cohort B, approximately 90 participants are planned. Assuming the true ORR is 30% for the intervention in this group, 90 participants are needed to ensure that there is at least 90% power to reject the null hypothesis of $ORR \leq 15\%$. This calculation assumes 1-sided test at the overall 0.025 level of significance.

For Cohort C, approximately 20 participants will be enrolled, which will provide at least 80% chance of observing at least 4 responders in this cohort if the underlying ORR is 30%.

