## **10. STATISTICS**

### **10.1. Sample Size Determination**

For Cohort A, approximately 60 participants are planned. Assuming the true ORR is 35% for the intervention in this group, 60 participants are needed to ensure that there is at least 90% power to test the null hypothesis of  $ORR \leq 15\%$ . This calculation assumes 1-sided test at the overall 0.025 level of significance.

For Cohort B, approximately 90 participants are planned. Assuming the true ORR is 30% for the intervention in this group, 90 participants are needed to endure that there is at least 90% power to test the null hypothesis of  $ORR \leq 15\%$ . This calculation assumes 1-sided test at the overall 0.025 level of significance.

For Cohort C, approximately 20 participants will be enrolled, which will provide at least 80% chance of observing at least 4 responders in this cohort if the underlying ORR is 30%.

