3.2. Control of Type I Error

For the primary endpoint, the overall 1-sided Type I error is 0.025. The primary endpoint in Cohort A and Cohort B will be tested sequentially at 1-sided 0.025. If ORR in Cohort A is significant, then ORR in Cohort B will be tested.

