7.2. Analysis of the Primary Efficacy Parameter

7.2.1. Primary Efficacy Analysis

The primary endpoints of the study are ORR in Cohort A and Cohort B, respectively. Objective response rate is defined as the proportion of participants who achieved a CR or a PR based on RECIST v1.1 or RANO, as assessed by an independent centralized radiological review committee. Confirmation of CR and PR is required and documented in the Independent Central Review Charter. This analysis will be based on the efficacy evaluable population. Participants

who do not have sufficient baseline or on-study response assessment information to be adequately assessed for response status will be included in the denominators in the calculation of ORR. The 95% CI for the ORR will be estimated using the Clopper-Pearson method. The p-value from the exact binomial test will be provided.

The ORR will also be analyzed based on the PP population as a sensitivity analysis.

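### The stated power of at least 90% for Cohort B leaves out the Cohort A gate; within the planned testing sequence it is about 87%

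*SAP*

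**What the plan says.** SAP 3.3 sizes each cohort separately. "For Cohort A, approximately 60 participants are planned", with a true ORR of 35% against a null of 15%. "For Cohort B, approximately 90 participants are planned", with a true ORR of 30% against the same null, and the SAP concludes that "90 participants are needed to ensure that there is at least 90% power to reject the null hypothesis". It adds for each cohort: "This calculation assumes 1-sided test at the overall 0.025 level of significance". Protocol 10.1 gives the same Cohort B figure, with slightly different verbs: "90 participants are needed to endure that there is at least 90% power to test the null hypothesis".

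The testing rule is in the section just before. SAP 3.2 states "For the primary endpoint, the overall 1-sided Type I error is 0.025" and sets a fixed order: "If ORR in Cohort A is significant, then ORR in Cohort B will be tested". Protocol 10.3 has the same rule. For the test itself, SAP 7.2.1 says "The p-value from the exact binomial test will be provided".

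Neither document gives a power for Cohort B within this order, and neither says that the stated figure is conditional on Cohort A.

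**The concern.** Under the fixed order, the Cohort B null can be rejected only if both tests succeed. The full one-sided 0.025 used in the Cohort B calculation is available to that cohort only once Cohort A has passed. The power statement uses that level but counts none of the cost of the gate. As a description of what the design delivers for Cohort B, it is therefore too high.

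Cohort B is one of the two primary endpoints. Someone judging the order of testing, or the chance of a formal Cohort B claim, would take the 90% as the design's figure. What is at stake is the accuracy of that description. The Type I error, the Cohort A power, and the Cohort B response rate and confidence interval that will be reported are not affected.

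**Working it through.** **Inputs.** Null ORR 15% in both cohorts (SAP 7.1); n = 60 and true ORR 35% for A, n = 90 and true ORR 30% for B (SAP 3.3, Protocol 10.1); one-sided 0.025 and A before B (SAP 3.2, Protocol 10.3); exact binomial test (SAP 7.2.1, Protocol 10.4.1). Participants who cannot be assessed stay in the denominator (SAP 7.2.1), so n is not reduced for them.

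**Step 1: the plan's own figures.** For each cohort, find the smallest r with P(X ≥ r | n, 0.15) ≤ 0.025. Power is then P(X ≥ r | n, true ORR).

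| Cohort | n | Reject at | Tail at 15% | Tail one responder lower | Power |
|---|---|---|---|---|---|
| A | 60 | 16 or more | 0.0136 | 0.0291 | 0.9344 at 35% |
| B | 90 | 21 or more | 0.0240 | 0.0434 | 0.9355 at 30% |

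Both meet the stated 90% as separate tests.

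**Step 2: Cohort B within the sequence.** Each participant is assigned to one cohort only (Protocol 5.1), so the two results are independent:

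P(reject B) = P(A significant) x P(B significant) = 0.9344 x 0.9355 = 0.8741.

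The shortfall against the stated minimum is 90.0 − 87.4 = 2.6 points. Independence also means that the power of B given that A is significant equals its stand-alone power, 93.5%.

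(A Wald approximation for Cohort B alone also happens to give 87.4%. That is a coincidence; the planned test is exact.)

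**Step 3: futility rules followed exactly.** SAP 9 and Protocol 10.5 allow stopping at 4 or fewer responders among about 25 in A, and 6 or fewer among about 35 in B. With f the stopping count, n1 the interim size, X1 the responders among those n1 and X2 the responders among the remaining n − n1, power is the sum over x from f + 1 to n1 of P(X1 = x) x P(X2 ≥ r − x). This gives 0.9169 for A and 0.8932 for B, and 0.9169 x 0.8932 = 0.819 in the sequence. The rules are nonbinding, so the main figure leaves them out.

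**Step 4: sensitivity.** Both sample sizes are approximate. The ranges below are assumptions, and the critical values are recomputed at each n.

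| Change from plan | Cohort B power in sequence |
|---|---|
| Both n within 3 (49 combinations) | 83.7% to 89.9%; none reaches 90% |
| Both n within 5 (121 combinations) | 81.7% to 91.4%; 6 reach 90% |
| True ORR in A 30% | 70.7% |
| True ORR in A 33% | 82.6% |
| True ORR in A 40% | 92.5% |

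The last three rows keep n = 60 and 90 and B at 30%.

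**The case against.** The strongest reply is that nothing stated is wrong. Giving power per hypothesis is an accepted convention. The Cohort B paragraph has its own n, null, level and effect, and assumes nothing about the response rate in Cohort A, which a sequence-wide figure would need. Its natural scope is therefore the single test, and the gate is set out openly in the preceding section. All of this stands: the figure is not a miscalculation, and a reader who infers an arithmetic error would be mistaken.

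It is also fair that 87% is no firmer than 90%. It moves with the realised sample sizes, with the true rate in Cohort A and with how the futility rules are used. That is a reason to print the assumptions beside it, not to omit it.

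The convention does not cover the wording. The SAP speaks of power to reject the Cohort B null, and its own rule blocks that rejection whenever Cohort A fails. Without a word on scope, the stated minimum is not what the testing rule delivers at the planned rates.

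**Conclusion.** The point holds as a minor matter of reporting. Cohort B has 93.5% power given that Cohort A is significant, and about 87% within the sequence. The second figure rests on true ORRs of 35% and 30%, on 60 and 90 participants, on independent cohorts and on no futility stopping. It is 2.6 points below the stated minimum; with both futility rules followed exactly it is about 82%.

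The documents do not support three stronger readings:

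- **That Cohort B is too small.** Its 90 participants meet the stated target for its own test. The shortfall comes from the gate.
- **That the sequence figure is hidden.** Every input needed to compute it is in the two documents; what is missing is the statement itself.
- **That the gate roughly doubles the risk of missing the Cohort B claim.** This sets 1 − 0.8741 = 12.6% against the 6.5% miss probability of the test alone. The plan never states 6.5%. It promises a miss probability of at most 10%, so the gap is again 2.6 points.

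**What to change.** In SAP 3.3 and Protocol 10.1, restate the Cohort B power. Suggested text:

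> Given that Cohort A is significant, 90 participants provide at least 90% power for the Cohort B test if the true ORR in Cohort B is 30%. Within the testing sequence, power for Cohort B is about 87% if the true ORR is 35% in Cohort A and 30% in Cohort B, with 60 and 90 participants. Both figures are without futility stopping.

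This changes a few sentences in one section of each document and can go with the next amendment. Sample sizes, testing order, thresholds and futility rules stay the same. The only downside is a slightly less favourable stated figure for Cohort B.

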3.4. Schedule of Assessments

Refer to Protocol Amendment 2 dated 14 JAN 2020 for a full description of all study procedures and assessment schedules for this study.

4. DATA HANDLING DEFINITIONS AND CONVENTIONS

4.1. Scheduled Study Evaluations and Study Periods

4.1.1. Day 1

Day 1 is the date that the first dose of pemigatinib is administered to the participants.

4.1.2. Study Day

If a visit/reporting date is on or after Day 1, then the study day at the visit/reporting date will be calculated as

$$\text{Day \#} = (\text{visit/reporting date} - \text{Day 1 date} + 1).$$

If the visit/reporting date is before Day 1, then the study day at the visit/reporting date will be calculated as

$$\text{Day \#} = (\text{visit/reporting date} - \text{Day 1 date}).$$

A study day of -1 indicates 1 day before Day 1.

4.1.3. Baseline Value

Baseline is the last nonmissing measurement obtained before the first administration of pemigatinib. When scheduled assessments and unscheduled assessments occur on the same day and time of the assessment or time of first dose is not available, use the following convention to determine baseline:

- If both a scheduled and an unscheduled visit are available on the day of the first dose and the time is missing, use the scheduled assessment as baseline.
- If all scheduled assessments are missing on the day of the first dose and an unscheduled assessment is available, use the unscheduled assessment as baseline.

4.1.4. Handling of Missing and Incomplete Data

In general, values for missing data will not be handled unless methods for handling missing dates are specified in this section or relevant sections. The original reported dates collected on the eCRF should be used in all relevant listings. The following rules will be used for handling partial dates for analyses requiring dates.

When calculating time since diagnosis of cancer, partial cancer diagnosis date will be handled as follows in the calculation:

- If only the day is missing, then use the first day of the month.
- If both the month and day are missing, then use 01 JAN of the year.
- Time since diagnosis will be missing if the diagnosis date is completely missing.

When date of last dose is used in deriving variables such as duration of treatment or TEAE flag, missing or partial date of last dose will be handled as follows:

- If only the day is missing, then use the earlier date of the last day of the month or the date that the participant discontinued treatment.
- Otherwise, the date that the participant discontinued treatment will be used as the date of the last dose.

For relevant efficacy endpoints, partial date of death will be handled as follows in the calculation:

- If mmYYYY for the last known alive date = mmYYYY for the death date, then the death date will be set to the day after the last known alive date.
- If mmYYYY for the last known alive date < mmYYYY for the death date, then the death date will be set to the first day of the death month.
- Otherwise, the partial death date will not be handled.

4.1.5. Cycle Length and Duration

Cycle 1 Day 1 is the day that the first dose of pemigatinib is administered. Scheduled cycle length is 21 days. Actual Day 1 of subsequent cycles will correspond with the first day of administration of pemigatinib in that cycle.

4.1.6. Analysis Window

For parameters that will be summarized by visit, the nominal visit as recorded on the eCRF will be used. There will be no additional analysis windowing done based on the assessment date.

4.2. Variable Definitions

4.2.1. Prior and Concomitant Medication

Prior medication is defined as any nonstudy medication started before the first dose of pemigatinib.

Concomitant medication is defined as any nonstudy medication that is started accordingly:

- Before the date of first administration of pemigatinib and is ongoing throughout the study or ends on/after the date of first study drug administration.
- On/after the date of first administration of pemigatinib and is ongoing or ends during the course of study drug administration.

A prior medication could also be classified as "both prior and concomitant medication" if the end date is on or after first dose of pemigatinib. In the listing, it will be indicated whether a medication is prior-only, concomitant-only, or both prior and concomitant.

For the purposes of analysis, all medications will be considered concomitant medications unless the medications can unequivocally be defined as not concomitant.

5. STATISTICAL METHODOLOGY

5.1. General Methodology

Unless otherwise noted, SAS® software (SAS Institute Inc, Cary, NC; v9 or later) will be used for the generation of all tables, graphs, and statistical analyses. Descriptive summaries for continuous variables will include, but not be limited to, the number of observations, mean, standard deviation, median, minimum, and maximum. Descriptive summaries for categorical variables will include the number and percentage of participants in each category.

Interim analyses are planned for this study as defined in Section 9.

5.2. Treatment Groups

This is an open-label, single-treatment group study. Participants will be summarized by treatment cohort and by total. Cohort determination will be based on FGFR mutation or gene rearrangement results from central genomics laboratory.

5.3. Analysis Populations

5.3.1. Efficacy Evaluable Population

The efficacy evaluable population includes all enrolled participants in Cohorts A, B, and C who received at least 1 dose of pemigatinib. The efficacy evaluable population will be used for analyses of all efficacy data.

5.3.2. Safety Population

The safety population includes all enrolled participants who received at least 1 dose of pemigatinib. The safety population will be used for the summary of demographics, baseline characteristics, participant disposition and all safety analyses.

5.3.3. Per Protocol Population

The PP population includes all efficacy evaluable population participants who are sufficiently compliant with the Protocol.

The following procedures will be performed to identify those participants who are to be excluded from the PP population :

- Clinical review of Protocol deviations
- Clinical review of concomitant medications as defined in Section 6.6 of the Protocol
- Clinical review of the dose administration and drug accountability listing

The determination of participants being considered for exclusion from the PP population by the clinical team will be prepared and signed before database freeze.

The PP population will be used in the supportive sensitivity analyses for efficacy endpoints.

5.3.4. RECIST Evaluable Population

The RECIST evaluable population includes all efficacy evaluable population participants who have at least 2 objective tumor response assessments per independent centralized radiological review or who discontinued from the study.

RECIST evaluable population will be used for ORR analysis in the interim.

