## 7. DISCONTINUATION OF STUDY TREATMENT AND PARTICIPANT DISCONTINUATION/WITHDRAWAL

### 7.1. Discontinuation of Study Treatment

#### 7.1.1. Reasons for Discontinuation

Participants **must** be discontinued from study treatment for the following reasons. Please note that if a participant discontinues study treatment for reasons other than disease progression or withdraw of consent, the participant should be followed until disease progression is documented.

- The participant becomes pregnant.
- Consent is withdrawn.  
Note: Consent withdrawn means that the participant has explicitly indicated that they do not want to be followed any longer; in this case no further data, except data in public domain, may be solicited from or collected on the participant. Participants may choose to discontinue study treatment and remain in the study to be followed for progression and survival.
- Further participation would be injurious to the participant's health or well-being, in the investigator's medical judgment.
- Unacceptable toxicity as noted in Section 6.5.
- The study is terminated by the sponsor.
- The study is terminated by the local health authority, IRB, or IEC.
- Disease progression has been reported by central radiology review.
- Other antineoplastic treatment is initiated, not including palliative radiation.

A participant **may** be discontinued from study treatment if a participant is noncompliant with study procedures or study drug/treatment administration in the investigator's opinion, the sponsor should be consulted for instruction on handling the participant.

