**Table 16: Populations for Analysis**

Population	Description
Efficacy evaluable	
The efficacy evaluable population includes all enrolled participants in Cohorts A, B, and C who received at least 1 dose of study drug.
 
The efficacy evaluable population will be used for the summary of demographics, baseline characteristics, participant disposition, and analyses of all efficacy data.

Safety	The safety population includes all enrolled participants who received at least 1 dose of study drug. All safety analyses will be conducted using the safety population.
Per protocol	The per protocol population includes all efficacy evaluable population participants who are sufficiently compliant with the Protocol.
RECIST/RANO evaluable	
The RECIST/RANO evaluable population includes all efficacy evaluable population participants who have at least 2 objective tumor response assessments per independent centralized radiological review or who discontinued from the study or who discontinued from treatment without post-treatment tumor assessments.
 
RECIST/RANO evaluable population will be used for ORR analysis in the interim.

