## **10.5. Interim Analysis**

For Cohort A, futility analysis will be performed when approximately 25 participants are enrolled into the cohort and have at least 2 objective tumor response assessments per independent centralized radiological review or are discontinued from the study or are discontinued from treatment without post-treatment tumor assessments. Cohort A can be stopped for futility if  $\leq 4$  responders are observed in RECIST/RANO evaluable population, for which there is  $< 10\%$  probability of claiming ORR  $> 15\%$  at final analysis. This rule is just a guidance and nonbinding.

For Cohort B, futility analysis will be performed when approximately 35 participants are enrolled into the cohort and have at least 2 objective tumor response assessments per independent centralized radiological review or are discontinued from the study or are discontinued from treatment without post-treatment tumor assessments. Cohort B can be stopped for futility if  $\leq 6$  responders are observed in RECIST/RANO evaluable population, for which there is approximately 14% probability of claiming ORR  $> 15\%$  at final analysis. This rule is just a guidance and nonbinding.

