## 27. Section 10.5, Interim Analysis

**Description of change:** Clarified that patients who are discontinued from treatment without post-treatment tumor assessments will be included in the interim analysis.

**Rationale for change:** Clarification requested by internal team.

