2. STUDY INFORMATION, OBJECTIVES, AND ENDPOINTS

2.1. Protocol and Case Report Form Version

This SAP is based on INCB 54828-207 Protocol Amendment 2 dated 14 JAN 2020 and CRFs approved on 12 APR 2020. Unless superseded by an amendment, this SAP will be effective for all subsequent Protocol amendments and eCRF versions.

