6.2. Disposition of Participant

The number and percentage of participants who were treated, who were ongoing with study treatment, who discontinued study treatment with a primary reason for discontinuation, who were still in study, and who withdrew from the study with a primary reason for withdrawal will be summarized for the safety population.

The number and percentage of participants who were screened and enrolled will be summarized.

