9. INTERIM ANALYSIS

For Cohort A, futility analysis will be performed when approximately 25 participants are enrolled into the cohort and have at least 2 objective tumor response assessments per independent centralized radiological review or are discontinued from the study. Cohort A can be stopped for futility if ≤ 4 responders are observed, for which there is $< 10\%$ probability of claiming ORR $> 15\%$ at final analysis. This rule is just a guidance and nonbinding.

For Cohort B, futility analysis will be performed when approximately 35 participants are enrolled into the cohort and have at least 2 objective tumor response assessments per independent centralized radiological review or are discontinued from the study. Cohort B can be stopped for futility if ≤ 6 responders are observed, for which there is approximately 14% probability of claiming ORR $> 15\%$ at final analysis. This rule is just a guidance and nonbinding.

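### The SAP and the current Protocol define the futility population differently, and neither definition matches the final ORR denominator (minor, since the rule is nonbinding)

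*SAP*

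**What the plan says.** Both documents plan a nonbinding futility look. Cohort A may stop with 4 or fewer responders in about 25 participants, and Cohort B with 6 or fewer in about 35. They differ on who is counted.

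- SAP 5.3.4 gives two routes into the interim population: "at least 2 objective tumor response assessments per independent centralized radiological review or who discontinued from the study". SAP 9 triggers the look on the same two routes: "at least 2 objective tumor response assessments per independent centralized radiological review or are discontinued from the study".
- Protocol Table 16 adds a third route, "or who discontinued from treatment without post-treatment tumor assessments", and Protocol 10.5 repeats it in the trigger: "or are discontinued from treatment without post-treatment tumor assessments". Appendix F dates the addition to Amendment 3 (15 FEB 2021): "Clarified that patients who are discontinued from treatment without post-treatment tumor assessments will be included in the interim analysis".
- The only SAP version listed is dated 23 SEP 2020 and is based on Amendment 2. SAP 2.1 adds: "Unless superseded by an amendment, this SAP will be effective for all subsequent Protocol amendments and eCRF versions". It does not say whether a Protocol amendment alone can supersede it.
- Stopping treatment is not leaving the study. Protocol 7.1.1 says "Participants may choose to discontinue study treatment and remain in the study to be followed for progression and survival", Protocol 8.8.2 and 8.8.3 provide disease and survival follow-up, and SAP 6.2 counts separately those "who were still in study, and who withdrew from the study with a primary reason for withdrawal".
- The final ORR (Protocol 10.4.1, SAP 7.2.1) is taken over all treated participants and keeps those who cannot be assessed in the denominator. SAP 7.2.1 requires responses to be confirmed.

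**The concern.** Two programmers, one working from the SAP and one from the Protocol, could build different datasets for the same 4/25 and 6/35 rules. Neither dataset is a sample of what the final analysis counts. The SAP can leave out a non-responder who stops before any scan and is alive in follow-up. The Protocol counts that person as soon as treatment stops, while participants treated at the same time wait about 18 weeks for two 9-weekly scans. The first pushes the interim ORR up and the second pushes it down. The probabilities attached to the boundaries (below 10% and about 14%) assume that the interim participants resemble the final ones. What is at stake is the advice on whether to continue enrolling a cohort.

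**Working it through.** **1. The plan's own figures.** Inputs: null ORR 15%, one-sided 0.025, N = 60 and 90, alternatives 35% and 30%. The exact binomial test needs at least 16/60 (alpha 0.0136, power 93.4%) and at least 21/90 (alpha 0.0240, power 93.5%). The documents do not name the method behind the boundary probabilities. A beta-binomial predictive probability with a prior centred on the alternative gives:
- Cohort A, 4/25, Beta(0.35, 0.65): at least 12 of the remaining 35, 6.1% (stated: below 10%).
- Cohort B, 6/35, Beta(0.30, 0.70): at least 15 of the remaining 55, 13.9% (stated: about 14%).

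The boundaries are sound for a representative interim group.

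**2. Who is counted.** Death and withdrawal are taken as discontinuing the study.

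| Participant | SAP interim | Protocol interim | Final ORR |
|---|---|---|---|
| Two ICR assessments | in | in | in |
| Died or withdrew | in | in | in |
| Off treatment, never scanned after baseline, alive in follow-up | out | in at once | in, non-responder |
| PD at the only postbaseline scan, alive on study | out, unless baseline counts as one of the two | out, unless baseline counts or *post-treatment* means after stopping | in, non-responder |

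**3. Upper-end static check.** If a net share d of treated participants, all non-responders, is left out, the interim ORR is p/(1 − d) and P(stop) is the binomial CDF at the boundary. At p = 15%:

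| d | 0 | 3% | 5% | 10% |
|---|---|---|---|---|
| A: P(X ≤ 4 of 25) | 68.2% | 65.8% | 64.1% | 59.4% |
| B: P(X ≤ 6 of 35) | 73.5% | 70.8% | 68.9% | 63.6% |

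This ignores re-entry when a stopper dies or withdraws, so it overstates the effect for any given share of stoppers.

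**4. SAP wording with re-entry.** Simulation, every input assumed: 5% or 10% stop unscanned, uniformly over weeks 1–9; others evaluable at week 18; accrual 0.6, 1 or 2 per week; exponential time to death or withdrawal; true ORR 15% over all treated; 4,000 runs per setting (Monte Carlo SE at most 0.8 points).

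| Median time to death or withdrawal | Interim ORR A | Interim ORR B | P(stop) A | P(stop) B |
|---|---|---|---|---|
| 26 weeks | 15.3–15.8% | 15.3–15.6% | 64.5–67.2% | 69.6–71.6% |
| 13 weeks | 14.8–15.2% | 14.9–15.2% | 67.3–69.9% | 71.8–74.0% |
| 4 weeks | 13.9–14.9% | 14.4–15.0% | 68.4–73.5% | 74.0–76.1% |

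The reference is 68.2% and 73.5%. The largest falls are 68.2 − 64.5 = 3.7 and 73.5 − 69.6 = 3.9 points, or about 4 to 5 allowing for simulation error. The net share left out was 0.1% to 5.8%.

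**5. Protocol wording, same model.** Unscanned stoppers enter at weeks 1–9 and others at week 18, so early non-responders are over-represented. At a true 15% the interim ORR is up to about 1.5 points too low. Wrongful stopping at the design alternatives, against the exact fixed-group values P(X ≤ 4 | 25, 0.35) = 3.2% and P(X ≤ 6 | 35, 0.30) = 6.5%, is about 3% to 7% in Cohort A and 7% to 11% in Cohort B.

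**6. PD at the only scan.** Suppose the two assessments must be postbaseline and a further 15% to 20% (assumed) have PD at the first scan. P(stop) under the SAP at a true 15% is then 51%–62% (A) and 58%–66% (B) at 26 weeks, 63%–67% and 66%–71% at 13 weeks, and 70%–76% and 73%–80% at 4 weeks. This depends on the reading chosen in step 2.

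**The case against.** The strongest reply is that this is mostly wording. Amendment 3 calls its change a clarification. SAP Table 2 lists study discontinuation for toxicity, which suggests that *study* is sometimes used where treatment is meant; on that reading the SAP already covers these participants. End-of-treatment scans, 9-weekly disease follow-up, death and withdrawal bring many of them back. SAP 7.2.1.1 assigns a response only at postbaseline assessments, which points to a postbaseline count. The rule is nonbinding and its sample sizes are approximate.

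Much of this stands, and it is why the point is minor. It does not remove the difference between two operative texts, since SAP 6.2 and Protocol 7.1.1 do separate treatment from study status.

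Three stronger readings are tempting, and the documents do not support them:

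- A reader might infer that the SAP is the biased text and the Protocol the correct one. Under the same assumptions the Protocol wording distorts the interim ORR by more, in the opposite direction.
- A reader might take the static 10% column (68% to 59% in Cohort A) as the effect. No document gives that share, and with 5% to 10% unscanned stoppers the net share left out did not exceed 5.8%.
- A reader might say that omission can only raise the interim ORR. With early death or withdrawal the SAP admits these non-responders ahead of others, and the effect reverses.

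**Conclusion.** The inconsistency is real and worth correcting, at minor severity. The two documents give different populations for one rule, precedence is not stated, and neither population matches the final ORR denominator. At a true ORR of 15% with 5% to 10% unscanned stoppers, the SAP wording shifts the interim ORR upward by at most about 0.8 points, and only when stoppers stay in follow-up for long. The cost of the Protocol wording falls on active cohorts: wrongful stopping can roughly double in Cohort A (3.2% to about 7%) and rise by about four points in Cohort B (6.5% to about 11%). All shares, accrual rates and follow-up times are assumptions.

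Two terms also need settling: whether *post-treatment* means after baseline or after treatment stops, and whether both assessments are postbaseline. On some readings a participant with PD at the only scan who is alive on study is left out, and step 6 shows that this could matter more than the third route. Type I error and the final ORR are unaffected.

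**What to change.** Put one definition, under one population name, in SAP 5.3.4 and 9 and in Protocol Table 16 and 10.5:

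- Apply 4/25 and 6/35 to the first 25 (Cohort A) or 35 (Cohort B) consecutively treated participants.
- Hold the look once each has had the opportunity for two postbaseline scans (about 18 weeks on the 9-weekly schedule) and any pending confirmatory scan is in.
- Count anyone in that group without a confirmed response as a non-responder, whatever their treatment or study status, as in the final ORR.
- State that assessments are postbaseline. *Post-treatment* is then no longer needed.
- State in SAP 2.1 which document governs if they differ.

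Copying the Protocol's third route into the SAP would end the contradiction but keep the early-admission bias, so it is not recommended alone.

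The cost is a wording change to both documents, including a Protocol amendment, with no new data. With 10% unscanned stoppers the simulated look comes about a week later than under the Protocol wording (for example, mean week 42.9 against 41.8 in Cohort A and 52.9 against 51.7 in Cohort B at 1 participant per week), plus at least 4 weeks if a confirmatory scan is pending.
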